10.2.3 Handling of Missing Data Not Related to Intercurrent Events

All data obtained in evaluable subjects/eyes will be included in the analysis. No imputation for missing values will be carried out for the primary and key exploratory efficacy analysis.

10.5 Safety Analyses

The safety endpoints are

- AEs
- BCVA
- Biomicroscopy findings
- Device deficiencies

There are no safety hypotheses planned in this trial. The focus of the safety analysis will be a comprehensive descriptive assessment of occurrence of adverse events as well as the other listed parameters.

[figure not shown]
All AEs occurring from the time a subject signs informed consent to study exit will be accounted for in the reporting. Safety analyses will be conducted using the safety analysis set on a treatment-emergent basis. Descriptive summaries (frequencies and percentages) for ocular and nonocular AEs will be presented by Medical Dictionary for Regulatory Activities Preferred Terms. AEs leading to study discontinuation and SAEs will be identified. Individual subject listings will be provided, as necessary.

Individual subject listings will be provided for AEs that occur after signing informed consent but prior to day of first exposure to IP.

Each biomicroscopy parameter will be summarized. For lens and status of lens biomicroscopy parameter, counts and percentages of eyes that experience an increase of ≥ 1 grade from baseline (last assessment prior to study product exposure) to any subsequent visit will be presented; all other parameters counts and percentages of eyes that experience an increase of ≥ 2 grades from baseline (last assessment prior to study product exposure) to any subsequent visit will be presented. A supportive listing will be generated which will include all biomicroscopy data from all visits for those eyes experiencing the increase.

Two listings for device deficiencies, prior to exposure of study product and treatment emergent, will be provided. Additionally, each device deficiency category will be tabulated.

No inferential testing will be done for safety analyses.

11 PROTOCOL DEVIATIONS

Per ICH E6 (GCP) R2 Section 4.5.1 the investigator/institution should conduct the study in compliance with the protocol agreed with the sponsor and, if required, by the regulatory authority and which was given approval/favorable opinion by IRB/IEC.

Protocol waivers or deviations from the protocol inclusion and exclusion criteria are not allowed because they can potentially jeopardize the scientific integrity of the study regulatory acceptability or Subject safety. Therefore, adherence to the criteria as specified in the protocol is essential.

The site will contact the sponsor for clarification of inclusion and/or exclusion criteria as needed prior to enrollment of the study subject. The sponsor or their representative will document clarification requests and responses. If a Subject does not meet any of the eligibility criteria, that Subject may not be enrolled into the study.

If the investigator feels that in his/her clinical judgment, it is necessary to promptly implement reasonable alternatives to, or deviations from, the protocol in consideration of the safety of study subjects, the sponsor is to be notified of these alternatives and deviations, and the reasons for such changes are to be documented in the study records. The investigator is to also notify his/her IRB/IEC of any such changes.

If a significant protocol deviation is identified by the investigator or through site monitoring activities, an immediate submission to the IRB/IEC may be required (as per IRB/IEC guidelines). The sponsor will assess any protocol deviation and decide whether any of these non compliance should be reported to the relevant competent authority as a serious breach of Good Clinical Practice (GCP) and the protocol. If per the relevant competent authorities' requirements, the protocol deviation is not required to be reported immediately but is still required to be notified to the IRB/IEC, the specific protocol deviation will be added to the annual progress report.

The sponsor will review, designate, and/or approve all protocol deviations prior to the database lock.

12 GENERAL CONSIDERATIONS: REGULATORY, ETHICAL, AND STUDY OVERSIGHT

12.1 Regulatory and Ethical Considerations

The study will be conducted according to this clinical protocol and will be governed by all applicable governmental rules and regulations concerning the conduct of clinical trials on human subjects. This includes, but is not limited to:

- The approval of IRB/IEC
- The Helsinki Declaration (World Medical Association 2013)
- US Code of Federal Regulations, Title 21
- International Conference on Harmonisation (ICH) Consolidated Good Clinical Practice Guideline (E6 R2)
- Standard operating procedures of the sponsor and any other vendors participating in the conduct of the trial
- EU Clinical Trials Regulation 536/2014 and EC local laws and regulations
- Obtaining prospective informed consent

The investigator must ensure that all personnel involved in the conduct of the study are qualified to perform their assigned responsibilities through relevant education, training, and experience. The investigator and all clinical study staff must conduct the clinical study in compliance with the protocol. The investigator is not allowed to deviate from the protocol except to protect the rights, safety, and wellbeing of human subjects under emergency circumstances. Emergency deviations may proceed without prior approval of the sponsor and the IRB/EC but shall be documented and reported to the sponsor and the IRB/EC as soon as possible. Deviations from this protocol, regulatory requirements, and/or GCP must be recorded and reported to the sponsor prior to database lock. If needed, corrective and preventive action should be identified, implemented, and documented within the study records. Failure to implement identified corrective and preventative actions may result in site closure by the sponsor. Use of waivers to deviate from the clinical protocol is prohibited.

Before clinical study initiation, this protocol, the ICF, any other written information given to subjects, and any advertisements planned for subject recruitment must be approved by an

IRB/IEC. The investigator must provide documentation of the IRB/IEC approval to the study sponsor. The approval must be dated and must identify the applicable protocol, amendments (if any), ICF, assent form (if any), all applicable recruiting materials, written information for subject, and subject compensation programs. The IRB/IEC must be provided with a copy of the IFU and IB, any periodic safety updates, and all other information as required by local regulation and/or the IRB/IEC. Any additional requirements imposed by the EC or regulatory authority shall be followed. At the end of the study, the investigator must notify the IRB/IEC about the study's completion. The IRB/IEC also must be notified if the study is terminated prematurely. Finally, the investigator must report to the IRB/IEC on the progress of the study at intervals stipulated by the IRB/IEC.

Voluntary informed consent must be obtained in writing from every subject. The obtaining of consent shall be documented before any procedure specific to the clinical investigation is applied to the subject.

The investigator must have a defined process in case a subject would like to withdraw their consent (s). The investigator is the designated contact point for any such withdrawals.

The investigator must have a defined process in case a subject would like to exercise any of their rights under applicable data protection laws. The investigator is the designated contact point for any such requests.

The study sponsor assures that the key designs of this protocol will be registered in a public database where required by current regulations, and, as applicable, results will be posted.

12.2 Committees

N/A

12.3 Informed Consent Process

Prior to any study procedures, the study will be discussed with each subject and subjects wishing to participate must give written informed consent including appropriate privacy authorization, as applicable. The verbal explanation of the study will cover all the elements specified in the written information provided for the subject. The investigator will inform the subject of the aims, methods, anticipated benefits, and potential hazards of the study, including any discomfort it may entail. The subject must be given every opportunity to clarify any points he/she does not understand and, if necessary, may ask for more information. At the end of the interview, the subject should be given time to reflect. The subjects and/or legally authorized representative then will be required to sign and date the ICF. Consent procedures

must follow local legal requirements of the study site. A copy of the signed and dated consent document will be given to each subject. The original signed and dated informed consent document must be maintained in the trial files at the investigator's site.

The investigator or staff is responsible for ensuring that no subject undergoes any study related examination or activity before the subject has given written informed consent. It should be emphasized that the subject is at liberty to withdraw consent to participate at any time, without penalty or loss of benefits to which the subject is otherwise entitled. Subjects who refuse to give, or withdraw, written informed consent may not be included or continued in this study and should be notified that discontinuation from the study will not impact their subsequent care.

If the subject is part of a vulnerable population, including without limitation minors, or requires any special needs, ensure that a parent or legal guardian signs the informed consent and that the subject signs an IRB/IEC-approved assent document as required.

12.4 Privacy and Data Protection

The investigator must ensure that the subject's identity is kept confidential throughout the course of the study. In particular, the investigator must maintain appropriate safeguards to prevent unauthorized use or disclosure of, or access to, subject data, and keep an enrollment log with confidential identifying information that corresponds to the subject numbers and initials of each study subject. The study sponsor may collect a copy of the enrollment log without any directly identifying subject information.

The study sponsor may share subject-level data collected in this study with qualified researchers to help facilitate product development or enhancements in research that is not directly related to the study objectives. The informed consent explains this to the study subject.

12.5 Early Site Closure or Study Termination

The study sponsor reserves the right to suspend or close the investigational site or suspend or terminate the study in its entirety at any time. The investigator may terminate the site's participation in the study for reasonable cause.

If the clinical study is prematurely terminated or suspended:

- The study sponsor must:

- Immediately notify the investigator(s) and subsequently provide instructions for study termination.
- Inform the investigator and the regulatory authorities of the termination/suspension and the reason(s) for the termination/suspension.
- The investigator must:
 - Promptly notify the IRB/IEC of the termination or suspension and of the reasons.
 - Provide subjects with recommendations for poststudy treatment options as needed.

13 GENERAL CONSIDERATIONS: RISK MANAGEMENT AND QUALITY ASSURANCE

13.1 Quality Tolerance Limits

Quality tolerance limits (QTLs) will be predefined through an internal risk management process and monitored on an ongoing basis, with documentation of QTLs that are met summarized in the CSR.

13.2 Data Quality Assurance

The study sponsor will secure agreement from all involved parties to ensure direct access to all study related sites, source data and documents, and reports for the purpose of monitoring and auditing by the study sponsor, and inspection by domestic and foreign regulatory authorities. Quality control will be applied to each stage of data handling to ensure that all data are reliable and have been processed correctly. Agreements made by the study sponsor with the investigator/institution and any other parties involved in the clinical study will be provided in writing as part of the protocol or as a separate agreement.

13.3 Source Data

The nature and location of all source documents will be identified to ensure that original data required to complete the CRFs exist and are accessible for verification by the site monitor, and all discrepancies shall be appropriately documented via the query resolution process. Site monitors are appointed by the study sponsor and are independent of study site staff.

If electronic records are maintained, the method of verification must be determined in advance of starting the study.

At a minimum, source documents include the following information for each subject:

- Subject identification (name, sex, race/ethnicity)
- Documentation of subject eligibility
- Date of informed consent
- Dates of visits
- Documentation that protocol-specific procedures were performed
- Results of study parameters, as required by the protocol
- IP accountability records
- Documentation of AEs and other safety parameters (if applicable)
- Records regarding medical histories and the use of concomitant therapies prior to and during the study
- Date of study completion and reason for early discontinuation, if applicable

It is required that the author of an entry in the source documents be identifiable. Direct access to source documentation (medical records) must be allowed for the purpose of verifying that the data recorded on the CRF are consistent with the original source data.

Only designated individuals at the site will complete the CRFs. The CRFs must be completed at regular intervals following the clinical study visit schedule. It is expected that all data reported have corresponding entries in the source documents. The principal investigator is responsible for reviewing and certifying that the CRFs are accurate and complete. The only subject identifiers recorded on the CRFs will be subject number, and subject demographic information.

A review of CRF data to the subject's source data will be completed by the site monitor to ensure completeness and accuracy. After the CRFs have been completed, additional data clarifications and/or additions may be needed as a result of the data cleaning process. Data clarifications are documented and are part of each subject's CRF.

14 APPENDIX: ADVERSE EVENTS AND SERIOUS ADVERSE EVENTS – DEFINITIONS, SEVERITY, AND CAUSALITY

14.1 Severity

Severity of an AE is defined as a qualitative assessment of the level of discomfort or the degree of intensity of an AE as determined by the investigator or reported to them by the subject. The assessment of severity is made irrespective of trial medication relationship or seriousness of the event and should be evaluated according to the following scale:

- 1 = Mild: present and noticeable, but not distressing, and no disruption of normal daily activities
- 2 = Moderate: bothersome, discomfort sufficient to possibly reduce or affect normal daily activity
- 3 = Severe: incapacitating, with inability to work or perform normal daily activity

A change in increased severity for a reported AE will require a stop date for the previous severity and a new start and stop date for the new severity. E.g., a change in severity may go from mild to moderate, or from moderate to severe. In either case, the start and stop dates should be recorded.

Note: A severe AE is not the same as a serious AE. Seriousness of an AE (NOT severity) serves as a guide for defining regulatory reporting obligations, if applicable.

14.2 Causality

Relationship between the AE and the trial intervention or trial procedure will be determined by the investigator, as applicable, for each AE using these explanations:

- Not Related: The event is clearly related to other factors such as subject's clinical condition, therapeutic interventions, concomitant disease, or therapy administered to the subject and does not follow a known response pattern to the product, device, or procedure.

- **Related:** The event follows a reasonable, temporal sequence from the time of trial medication administration or trial procedure and/or follows a known response pattern to the product, device or procedure and cannot be reasonably explained by other factors such as subject's clinical state, therapeutic interventions or concomitant therapy administered to the subject, and either occurs immediately following trial medication administration or procedure, or improves on stopping the trial medication, or reappears on repeat exposure, or there is a positive reaction at the application site.

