1 GLOSSARY OF TERMS

Table 1-1 List of Terms

Term	Definition
Adverse Drug Reaction (ADR)	All noxious and unintended responses to an investigational product related to any dose should be considered adverse drug reactions. Responses to a medicinal product means that a causal relationship between a medicinal product and an adverse event is at least a reasonable possibility, i.e., the relationship cannot be ruled out.
Adverse Event (AE)	Any untoward medical occurrence in a subject or clinical investigation subject administered a pharmaceutical product and which does not necessarily have a causal relationship with this treatment. An AE can therefore be any unfavorable and unintended sign (including an abnormal laboratory finding), symptom, or disease temporally associated with the use of an investigational product, whether or not related to the investigational product.
Device Deficiency	Inadequacy of a medical device with respect to its identity, quality, durability, reliability, usability, safety, or performance. Note: This definition includes malfunctions, use errors, and inadequacy in the information supplied by the manufacturer including labelling related to the investigational medical device.
Enrollment	A human subject's, or their legally authorized representative's, agreement to participate in a clinical trial following completion of the informed consent process, as required in 21 CFR part 50 and/or 45 CFR part 46, as applicable. For the purposes of this part, potential subjects who are screened for the purpose of determining eligibility for a trial, but do not participate in the trial, are not considered enrolled, unless otherwise specified by the protocol. A subject is enrolled at the time point they begin receiving the study investigational product.
Interventional Clinical Trial	Clinical trial in which subjects are assigned to groups that receive one or more intervention/treatment (or no intervention) so that researchers can evaluate the effects of the interventions on biomedical or health-related outcomes. The assignments are determined by the study's protocol. Subjects may receive diagnostic, therapeutic, or other types of interventions.

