9.4 Adverse Events and Serious Adverse Events

9.4.1 Definitions of AE and SAE

The following definitions of terms apply to this section:

- Adverse event (AE): Any untoward medical occurrence in a patient or clinical investigation subject administered a pharmaceutical product and which does not necessarily have a causal relationship with this treatment. An AE can therefore be any unfavorable and unintended sign (including an abnormal laboratory finding), symptom, or disease temporally associated with the use of a medicinal (investigational) product, whether or not related to the medicinal (investigational) product.
- Adverse drug reaction (ADR): All noxious and unintended responses to a medicinal product related to any dose should be considered ADRs. Responses to a medicinal product means that a causal relationship between a medicinal product and an adverse event is at least a reasonable possibility, i.e., the relationship cannot be ruled out.
- Adverse Event of Special Interest (AESI): Adverse event (serious or nonserious) of scientific and medical concern specific to the sponsor's product or program, for which ongoing monitoring and rapid communication by the investigator to the sponsor can be appropriate. Such an event might warrant further investigation in order to characterize and understand it. Depending on the nature of the event, rapid communication by the trial sponsor to other parties (e.g., regulators) might also be warranted.
- Life-threatening AE or life-threatening ADR: an AE or ADR is considered "life-threatening" if, in the view of either the investigator or sponsor, its occurrence places the subject at immediate risk of death. It does not include an AE or ADR that, had it occurred in a more severe form, might have caused death.
- Serious adverse event (SAE) or serious adverse reaction (SAR): an AE or AR is considered "serious" if, in the view of either the investigator or sponsor, it results in any of the following outcomes:
 - Death, a life-threatening or sight-threatening AE,

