- Suspected unexpected SAR (SUSAR): Adverse drug reaction that is both unexpected and meets the definition of a serious adverse event.
- Unexpected AE or unexpected ADR: an AE or ADR is considered “unexpected” if it is not listed in the IB or is not listed at the specificity or severity that has been observed; or, if an IB is not required or available, is not consistent with the risk information described in the general investigational plan or elsewhere in the current application, as amended.

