9.4.6 Reporting of SAEs

An investigator must immediately (i.e., within 24 hrs) report any SAE or SAR to the sponsor or sponsor representative, whether or not considered trial intervention-related, including those listed in the protocol or IB. The investigator must use the SAE report form (eCRF or email as a back-up) and include an assessment of whether there is a reasonable possibility that the trial intervention caused the event. The investigator must report any SAE or SAR that occurs or is observed during the trial. In case of incomplete information, the investigator must provide follow-up information as soon as possible, again using the SAE report form. The details for SAE/SAR report submission are listed below.

Report SAEs/SARs within 24 hrs via electronic data capture (EDC) system or, in the case of the EDC system not being available, the provided SAE source document will be completed and sent via the instructions noted on the form to the sponsor representative within the expected reporting time frame.

SAE/SAR reports will be evaluated by the medical monitor. Regulatory authorities, IRB/IEC, and investigators at each of the trial sites will be informed as required.

An assessment of seriousness will also be performed for all adverse events by a sponsor physician utilizing the same criteria. If an adverse event reported for an investigator's subject is upgraded to a serious adverse event by a sponsor physician, the investigator will receive a notification from the sponsor.

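### The two causality categories in Protocol 14.2 leave a gap, and *Related* is narrower than the protocol's own adverse drug reaction definition

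*Protocol*

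**What the plan says.** Protocol section 9.4.4 requires severity and relationship to be documented for adverse events and sends the reader to Appendix 14 for both AEs and SAEs. Section 14.2 then offers two categories.

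- *Not Related* begins "The event is clearly related to other factors" and adds that the event "does not follow a known response pattern to the product, device, or procedure". Both parts are needed.
- *Related* asks for plausible timing and/or a known response pattern, and that the event "cannot be reasonably explained by other factors". It also asks for one of four features: immediate onset, improvement when the product is stopped, recurrence on re-exposure, or a reaction at the application site.

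Elsewhere the protocol uses a wider test. Table 1-1 defines an adverse drug reaction as one where a causal link "is at least a reasonable possibility, i.e., the relationship cannot be ruled out", and section 9.4.1 repeats this. Section 9.4.6 tells the investigator reporting an SAE to "include an assessment of whether there is a reasonable possibility that the trial intervention caused the event". Section 9.4.1 defines a SUSAR as an "Adverse drug reaction that is both unexpected and meets the definition of a serious adverse event".

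**The concern.** A two-category scale works only if each category is what the other is not. Here both are demanding, so an event can fail both. The typical case is an event with a believable link to the drop and a competing explanation that is possible but not clear. Under Table 1-1 and section 9.4.1 that event is an adverse drug reaction, because the link cannot be excluded. Under section 14.2 it need not be *Related*, and it is not *Not Related* either. The investigator must still record something.

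The study is single-arm and uncontrolled (Protocol 2.1.2), so no comparator rate helps to separate product effects from disease. For non-serious events the investigator's attribution is the only causality judgement that the protocol describes; the medical monitor's evaluation in section 9.4.6 concerns SAE and SAR reports. If sites resolve the gap differently, the relatedness data are inconsistent and do not match the protocol's own definition of a reaction.

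**Working it through.** No sample size, power or event figure is involved, so the check is one of logic. I described an event by four attributes drawn from section 14.2:

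- T: timing plausible (yes/no)
- K: known response pattern (yes/no)
- S: at least one of the four supporting features (yes/no)
- A: alternative explanation (none / possible / clear), where a possible alternative counts as one that could reasonably explain the event

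This gives 2 × 2 × 2 × 3 = 24 profiles.

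The *Related* sentence joins its parts with an and/or followed by further ands, so I read it two ways.

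- *Not Related* = (A clear) and (not K)
- *Related*, strict = (T or K) and (A none) and S
- *Related*, lenient = [T or (K and A none)] and S

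**Counts over all 24 profiles**

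- *Not Related*: A clear, K no, T either way, S either way: 2 × 2 = 4.
- *Related*, strict: three T/K combinations with at least one yes, A none, S yes: 3. No profile meets both definitions. Neither: 24 − 3 − 4 = 17.
- *Related*, lenient: T yes and S yes gives 2 × 3 = 6; T no, K yes, A none, S yes adds 1; total 7. One profile (T yes, K no, S yes, A clear) meets both definitions. Neither: 24 − (7 + 4 − 1) = 14.

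**Counts over the profiles at issue** (T or K, with A possible): 3 × 2 = 6.

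| Reading | Related | Not Related | Neither |
|---|---|---|---|
| Strict | 0 | 0 | 6 |
| Lenient | 2 | 0 | 4 |

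The 2 under the lenient reading are the profiles with T yes and S yes.

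The gap is present on both readings; only its size depends on the parse. All 6 profiles meet the test in Table 1-1 and section 9.4.1, since a plausible link with only a possible alternative cannot be ruled out. So *Related* is narrower than the adverse drug reaction definition on either reading.

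**A concrete case.** Section 3.2.2 names transient blur and ocular discomfort as risks of the drop, and section 8.1.3 adds redness. Take new ocular discomfort in a subject whose dry eye might also explain it. It follows a known pattern, so it cannot be *Not Related*, whatever the other cause. On the strict reading the possible dry-eye explanation stops it being *Related*. On the lenient reading it is *Related* only if timing is plausible and a supporting feature is present. Section 8.1.3 rules out rechallenge after discontinuation for an AE, which limits one of those features.

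**Serious events.** For one SAE the investigator may answer yes to the reasonable-possibility question of section 9.4.6 and still be unable to choose *Related* under section 14.2. The protocol does not say which answer governs.

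**The case against.** A reader might infer that adverse reactions and SUSARs are bound to be under-counted. The documents do not support that, for three reasons.

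First, the direction of error is open. *Not Related* is restrictive too, and the anticipated reactions are barred from it by the known-pattern clause. A site forced to choose could go to *Related* as easily as to *Not Related*. Under-counting follows only if sites treat *Related* as the test and default everything else to *Not Related*.

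Second, a SUSAR is defined through the adverse drug reaction term, which carries the wide threshold. Every SAE must be reported within 24 hours regardless of causality (sections 9.4.6 and 14.3), the SAE report asks about reasonable possibility, and the medical monitor evaluates it. What stands is narrower: section 9.4.8 expects the site to recognise a SUSAR, and two thresholds are available for doing so.

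Third, the documents do not say that the disease nearly always offers an alternative explanation. Under section 9.4.10 unchanged symptoms are not AEs, and a pre-existing condition becomes one only when it worsens beyond its expected course.

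It can also be said that little depends on the field. The AE tables listed in SAP 5.3.1 are not split by relationship, there are no safety hypotheses, and section 9.4.7 states no health-authority SAE reporting requirement. The manual of procedures and eCRF guidance are not available here and might clarify the scale. All of this limits the consequence. It does not remove a rule that contradicts the protocol's own definition.

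**Conclusion.** The point holds as an inconsistency that should be corrected before relatedness is reported. The categories in section 14.2 are not exhaustive, and *Related* is narrower than Table 1-1, section 9.4.1 and the SAE question in section 9.4.6. Events with a plausible link and a possible alternative fit neither category always on the strict reading and in 4 of 6 profiles on the lenient one.

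The main exposure is non-serious adverse reactions, which may be misclassified in either direction. For serious events the risk is two conflicting causality answers, not a missed report. SAE capture, all-causality AE incidence and the primary endpoint are unaffected. The number of affected events cannot be estimated, because the documents give no AE rates and the profile counts are not frequencies.

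The conclusion assumes that investigators apply section 14.2 as written and that no document outside the protocol and SAP overrides it.

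**What to change.** Rewrite the two categories in section 14.2 as complements at the threshold that the protocol already uses, so that Table 1-1 and sections 9.4.1, 9.4.6 and 14.2 agree:

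- *Related*: there is a reasonable possibility that the product or procedure caused the event; the link cannot be excluded.
- *Not Related*: there is no such reasonable possibility.

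Keep timing, response pattern, improvement on stopping, recurrence on re-exposure and application-site reaction as considerations that inform the judgement, not as required conditions.

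The cost is one appendix paragraph and matching eCRF guidance. No endpoint, sample size or study procedure changes. The number of AEs recorded as related may change.
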